## 11.2 Summary of Laboratory Results

Routine clinical laboratory data (ie, hematology and serum chemistry) will be processed by local laboratories and entered directly into the electronic data capture system by site users. Atara Biotherapeutics will convert the original test results/units to standard and conventional results/units and grade lab test results based on the CTCAE version 5.0 grading and corresponding normal ranges for the lab parameters.

In case the lab test result is less than the lower limit of quantification (LLOQ), a value of half the LLOQ will be used for analysis and summary. If the lab test result is greater than the upper limit of quantification (ULOQ), the ULOQ will be used for analysis and summary. Lab test normal

range from University of California at San Francisco (UCSF) Clinical Laboratories Online Manual standards will be adapted.

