7.2 Laboratory Assessments

7.2.1 Local Laboratory Tests

Routine safety laboratory tests will be performed by local laboratories and results from these tests will be reported.

A serum pregnancy test will be performed.

CMV antibody will be collected at the study sites and analysis will be performed by the local laboratory.

The hematology panel will comprise the following parameters: CBC (red blood cells, hematocrit, hemoglobin, white blood cells) with differential (absolute neutrophils, lymphocytes, monocytes, eosinophils, and basophils) and platelets.

The coagulation panel will comprise the following parameters: PT, aPTT, and INR.

[figure not shown]
[figure not shown]
[figure not shown]
The full chemistry panel will comprise the following standard parameters: sodium, potassium, chloride, total carbon dioxide, BUN, creatinine, glucose (fasting), total calcium, albumin, total protein, serum creatinine, TBIL, ALT, AST, alkaline phosphatase, and tests of thyroid function (TSH, T3, and T4).

The abbreviated chemistry panel will consist of serum creatinine, TBIL, ALT, AST, alkaline phosphatase, glucose (fasting) and tests of thyroid function (TSH, T3, and T4).

High resolution HLA typing is comprised of DNA-level data for HLA-A, -B, -C, -DRB1, and -DQB1. Historical high-resolution HLA typing data are acceptable; but if these data are not available, high resolution typing will be performed so that HLA matching can be determined prior to enrollment.

7.2.2 *Central Laboratory Tests*

A tumor/active site core needle, incisional or excisional biopsy is required; fine needle aspirate is not for the purposes of this biopsy; hematology and coagulation panels must be performed prior to biopsy. Subjects for whom a new biopsy cannot be obtained (eg, inaccessible or subject safety concern) may submit an archived specimen only upon agreement from the sponsor. **CCI**

Samples will be collected and shipped to a central laboratory according to the instructions in the Laboratory Manual.

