7.2.3 Reporting Routine Laboratory Abnormalities

Laboratory test results along with appropriate normal ranges are to be reported routinely in the appropriate electronic data capture form. In addition, the investigator is responsible for reviewing laboratory test results and determining whether they meet AE reporting criteria (see Section 8), in which case they are to be reported on the adverse event form as well.

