### **2.1.3 Exploratory Objectives**

## **2.2 The exploratory analyses will be conducted adhoc upon request and are not described in this analysis plan. Study Design**

This is a multicenter, open-label, single-arm study in subjects with platinum-pretreated, recurrent/metastatic EBV+ NPC (also referred to as NPC in this protocol). The study was originally planned to be conducted in 2 parts as following: Cohort 1 will be enrolled as the phase 1B portion to determine the phase 2 dose; Cohort 2 will be enrolled as the phase 2 portion to examine the clinical benefits of combined T cell and checkpoint inhibitor immunotherapies for the treatment of subjects with NPC. The study will enroll 48 to 60 subjects in total. Phase 1B (Cohort 1) will enroll 12 to 24 subjects. For each dose level explored in Cohort 1, at least 6 subjects must have had disease that is refractory to PD-1 or PD-L1 monoclonal antibody. All other subjects enrolled to Cohort 1 will be checkpoint inhibitor naïve subjects (have never received pembrolizumab or other anti-PD-1, anti-PD-L1, anti-PD-L2, anti-CD137, anti-OX40 [CD134] or anti-CTLA-4 products). Dose de-escalation is permitted in Cohort 1 only. Cohort 2 will enroll 36 subjects who are checkpoint inhibitor naïve. Tabelecleucel was selected for each subject from the bank of available tabelecleucel cell products based on matching  $\geq 2$  HLA alleles, at least one of which is a restricting HLA allele, ie, shared between the tabelecleucel source material (donor) and the subject.

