### **11.2.1 General presentation of laboratory data**

Descriptive summaries of laboratory data will be provided for the Full Analysis Set and will include only data collected up to the last dose of study treatment plus 30 days.

For selected lab parameters, summaries of actual values, changes from baseline and percent changes from baseline for the postbaseline laboratory data will be presented for each scheduled assessment time point. Minimum and maximum post baseline values will be summarized. In the case of multiple values at the same visit, the assessment closest to the corresponding previous dose date will be used for summary purposes, unless specified otherwise. If either the baseline or post-baseline value is missing, the observation will not be included in the change from baseline summary.

In addition, grade shifts from baseline to the worst on-treatment value will be summarized for selected lab parameters.

For laboratory tests with criteria for both increased and decreased levels, analyses for each direction (ie, increased, decreased) will be presented separately.

Laboratory test results at unscheduled visits will be included in the summary of minimum and maximum post baseline values and the worst post baseline grade, but not in the by-visit summary.

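### SAP 11.2 appears to grade results from several local laboratories against one institution's normal range, so range-based laboratory grades can be too high or too low

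*SAP*

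**What the plan says.** **Where samples are assayed.** Protocol 7.2.1: "Routine safety laboratory tests will be performed by local laboratories and results from these tests will be reported". SAP 11.2 agrees: "Routine clinical laboratory data (ie, hematology and serum chemistry) will be processed by local laboratories". SAP 2.2 describes the trial as multicentre ("This is a multicenter, open-label, single-arm study in subjects with platinum-pretreated, recurrent/metastatic EBV+ NPC"). The number of sites is not given.

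**Which ranges are collected.** Protocol 7.2.3: "Laboratory test results along with appropriate normal ranges are to be reported routinely in the appropriate electronic data capture form".

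**Who grades, and against what.** Under SAP 11.2 the sponsor converts units and will "grade lab test results based on the CTCAE version 5.0 grading and corresponding normal ranges for the lab parameters". The next paragraph of the same section says that the normal "range from University of California at San Francisco (UCSF) Clinical Laboratories Online Manual standards will be adapted". It gives no reason, does not limit this to missing local ranges, has no rule for age, sex or assay method, and plans no sensitivity analysis with local ranges.

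**Where the grades go.** In SAP 11.2.1, "grade shifts from baseline to the worst on-treatment value will be summarized for selected lab parameters", and the worst post-baseline grade is also summarised. SAP 11.2.2 calls an abnormality treatment-emergent if it rises by at least one grade from baseline. If the baseline is missing, any abnormality of at least grade 1 counts. The SAP appendix lists ten tests for the abnormality and shift tables: leukocytes, platelets, neutrophils, lymphocytes, hemoglobin, creatinine, total bilirubin, AST, ALT and alkaline phosphatase.

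**The concern.** A result expressed as a multiple of ULN has meaning only against the range of the assay that produced it. Converting units to a common scale does not remove differences between laboratories' limits. If the sponsor divides a local result by another institution's ULN, the multiple changes although the patient has not, and a grade boundary can be crossed.

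The exposed tests are those graded relative to a limit of normal. The documents do not reproduce the CTCAE cut-offs. The protocol itself, however, states thresholds for creatinine, bilirubin, AST and ALT (inclusion criterion 11) and alkaline phosphatase (Section 8.2.1) as multiples of ULN, so these five are the natural examples.

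The safety profile is a primary objective, and the SAP introduction says the study ended in Phase 1B with 12 subjects. The laboratory tables are therefore a visible part of what will be reported. They may also differ from judgements investigators made on the same results with their local ranges.

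**Working it through.** The plan states no figure on this point, so there is none to reproduce. What can be checked is how a change of range acts on a result.

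**Inputs.**
- k = result as a multiple of the local ULN (illustrative values).
- c = common ULN divided by local ULN. Neither limit is in the documents, so c from 0.7 to 1.4 is an assumption.
- n = 12 subjects (SAP introduction).

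**Formula.** Against the common range the result reads k / c. The same form applies at the lower limit, with c as the ratio of the LLNs.

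**Results.**

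| Result against local ULN (k) | c | Reads as (k / c) | Effect |
|---|---|---|---|
| 0.95 | 0.7 | 0.95 / 0.7 = 1.36 | normal locally, counted as above normal |
| 0.95 | 0.8 | 0.95 / 0.8 = 1.19 | same |
| 0.95 | 0.9 | 0.95 / 0.9 = 1.06 | same |
| 1.2 | 1.25 | 1.2 / 1.25 = 0.96 | above normal locally, counted as normal |
| 1.2 | 1.4 | 1.2 / 1.4 = 0.86 | same |
| 2.5 | 0.7 | 2.5 / 0.7 = 3.57 | multiple overstated |
| 2.5 | 1.4 | 2.5 / 1.4 = 1.79 | multiple understated |
| any | 1.0 | k | unchanged |

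In general, at a boundary of m x ULN, results between m and m x c times the local ULN fall on the wrong side. The error runs upward when c is below 1 and downward when c is above 1.

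**Does using the same range at baseline and follow-up cancel the error?** No, because the boundaries are fixed.
- With c = 0.7, a subject moving from 0.6 to 0.95 x local ULN stays normal locally. Against the common range the subject moves from 0.6 / 0.7 = 0.86 to 1.36 and appears to become abnormal.
- With c = 1.4, a subject moving from 0.9 to 1.2 x local ULN becomes abnormal locally. Against the common range the subject moves from 0.9 / 1.4 = 0.64 to 0.86 and appears to stay normal.

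**Effect on an incidence.** One reclassified subject moves it by 1 / 12 = 8.3 percentage points. This is the step size, not an estimate of how many subjects would be reclassified.

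**The case against.** Five arguments can be made for leaving the text alone.

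1. **The SAP never says that local ranges are discarded.** It speaks of adapting the reference range, and the paragraph before refers to the ranges that correspond to the parameters. This stands as a limit on wording: a reader might infer an explicit replacement, and the text does not state one. But it does not confine the outside range to gaps either, and single-range grading is its natural reading.

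2. **The outputs that drive decisions are untouched.** This stands. A reader might infer that DLTs, adverse event grades, eligibility or the liver event of special interest would be misgraded. Protocol 5.2.3 and 9.3 leave DLT and adverse event grading to the investigator, and eligibility is settled before treatment. The liver event is a compound criterion (AST or ALT, bilirubin and alkaline phosphatase together). SAP 11.1 tabulates it among reported adverse events by preferred term, and nothing says it is derived from sponsor-graded laboratory values. Actual values, changes, percent changes, minima and maxima use no range.

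3. **One common range gives each subject a fixed yardstick**, so a shift cannot arise from a change of laboratory. That is a real advantage, but it does not rescue the rule. The yardstick does not belong to the assay, and fixed boundaries do not cancel the error.

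4. **The tables are descriptive and cover 12 subjects.** True, and this limits the consequence. It does not make a wrong grade right.

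5. **The protocol instructs sites to report ranges; it does not show that they are complete or specific to each sample.** Also true, and the reason a fallback is needed.

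**Conclusion.** The concern holds for sponsor-derived laboratory grades that depend on ULN or LLN. Followed as naturally read, SAP 11.2 can make these grades too high or too low in the grade-shift, worst-grade and treatment-emergent abnormality tables. They may then differ from investigators' local-range judgements; the documents do not show that they will.

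The actual error cannot be computed, since the documents give neither the reference limits nor any local limits. The movements shown above rest on the assumed ratio of 0.7 to 1.4. Where a local laboratory's limits equal the reference limits there is no effect, and any criterion fixed in absolute units is unaffected.

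The point is worth correcting because the remedy is specific and uses ranges the protocol already asks for. It does not threaten the DLT endpoint or any efficacy result.

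**What to change.** In SAP 11.2, replace the sentence on the reference range with wording such as:

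> Laboratory grades that depend on ULN or LLN use the normal range reported by the performing local laboratory for that sample. The single reference range is used only when the local range is missing, and results graded in this way are flagged.

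It would help to add that any fallback range is matched to age and sex where needed, since subjects may be as young as 12, and to report how many results were graded on it.

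**Cost.** A SAP wording change and use of the range data that Protocol 7.2.3 requires. Those data must be cleaned. A subject's range may also change if the laboratory changes, so an occasional grade shift could reflect that change. No change to trial conduct or clinical management is needed.

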### **11.2.1 General presentation of laboratory data**

Descriptive summaries of laboratory data will be provided for the Full Analysis Set and will include only data collected up to the last dose of study treatment plus 30 days.

For selected lab parameters, summaries of actual values, changes from baseline and percent changes from baseline for the postbaseline laboratory data will be presented for each scheduled assessment time point. Minimum and maximum post baseline values will be summarized. In the case of multiple values at the same visit, the assessment closest to the corresponding previous dose date will be used for summary purposes, unless specified otherwise. If either the baseline or post-baseline value is missing, the observation will not be included in the change from baseline summary.

In addition, grade shifts from baseline to the worst on-treatment value will be summarized for selected lab parameters.

For laboratory tests with criteria for both increased and decreased levels, analyses for each direction (ie, increased, decreased) will be presented separately.

Laboratory test results at unscheduled visits will be included in the summary of minimum and maximum post baseline values and the worst post baseline grade, but not in the by-visit summary.

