 - Grade 4 thrombocytopenia of any duration
 - Grade 3 thrombocytopenia associated with bleeding that requires a platelet transfusion
- Any nonhematologic AE grade ≥ 3 in severity should be considered a DLT, with the following exceptions: grade 3 fatigue lasting ≤ 3 days; grade 3 diarrhea, nausea, or vomiting without use of anti-emetics or anti-diarrheals per standard of care; grade 3 rash without use of corticosteroids or anti-inflammatory agents per standard of care.
- Any grade 3 or grade 4 non-hematologic laboratory value if:
 - Clinically significant medical intervention is required to treat the subject, or
 - The abnormality leads to hospitalization, or
 - The abnormality persists for > 1 week.
 - The abnormality results in a Drug-induced Liver Injury (DILI)
 - Exceptions: Clinically nonsignificant, treatable, or reversible laboratory abnormalities including liver function tests, uric acid, etc.

- Febrile neutropenia grade 3 or grade 4:
 - Grade 3 is defined as ANC < 1000/mm³ with a single temperature of > 38.3 degrees C (101 degrees F) or a sustained temperature of ≥ 38 degrees C (100.4 degrees F) for more than 1 hour
 - Grade 4 is defined as ANC < 1000/mm³ with a single temperature of > 38.3 degrees C (101 degrees F) or a sustained temperature of ≥ 38 degrees C (100.4 degrees F) for more than 1 hour, with life-threatening consequences and urgent intervention indicated.
- Prolonged delay (> 2 weeks) in initiating Cycle 2 due to treatment-related toxicity.
- Any treatment-related toxicity that causes the subject to discontinue treatment during Cycle 1.
- Missing > 25% of pembrolizumab or tabelecleucel doses as a result of investigational product-related AE(s) during the first cycle.
- Grade 5 toxicity.

Any subject experiencing any DLT will be withdrawn from treatment (both investigational products). Whenever possible, protocol-defined follow-up will be continued after the subject has discontinued investigational product treatment (refer to Section 6.7).

MTD definition: The MTD is defined as the highest dose level at which the subject incidence of a DLTs during the first 21-day cycle of investigational product dosing is < 33%.

RP2D definition: The RP2D is no higher than the MTD and is based on optimal benefit-risk, as determined by the SDRC.

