- **Cohort 1, Day 15 only**, Full chemistry panel: sodium, potassium, chloride, total carbon dioxide, BUN, creatinine, glucose (fasting), total calcium, albumin, total protein, serum creatinine, TBIL, ALT, AST, alkaline phosphatase, and tests of thyroid function (TSH, T3, and T4)
- **Cohort 2, at least 1 day after Cycle 1 Day 8 and prior to Cycle 1 Day 15 optional** tumor/active site biopsy as described in Section 7.2 (central laboratory); hematology and coagulation panels must be performed prior to biopsy
- **Cycle 1 and Cycle 2 Day 15 only:** CCI
[REDACTED]
[REDACTED]
[REDACTED]
- Investigational product infusion: tabelecleucel
- Vital signs (body temperature, BP, HR, and respiratory rates) at the following times:
 - immediately before the infusion
 - within 10 minutes following the conclusion of the infusion
 - 1 hour (\pm 10 minutes) after initiation of the infusion
 - If the subject experiences symptoms/signs of an infusion reaction, follow-up may be longer, as clinically indicated.

6.3.3 **Treatment/Consolidation, Observation: Days 16 to 21**

Between Days 16 to 21 of each cycle, the following *required* assessments/procedures will be performed:

- Concomitant medications
- AEs
- **Cycle 2 and subsequent cycles:** Radiographic assessments (MRI or CT with contrast) as described in Section 7.1

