6.5 End-of-Treatment Visit

An End-of-Treatment visit will be performed 30 ± 5 days after the last dose of investigational product (tabelecleucel and/or pembrolizumab) for all subjects, including those who discontinue early from treatment, consolidation, and/or maintenance. The following assessments/procedures will be performed:

- Physical examination including weight
- Concomitant medications
- AEs
- Vital signs (body temperature, BP, HR, and respiratory rate)
- Hematology: CBC with platelet count and differential
- Full chemistry panel: sodium, potassium, chloride, total carbon dioxide, BUN, creatinine, glucose (fasting), total calcium, albumin, total protein, serum creatinine, TBIL, ALT, AST, alkaline phosphatase, and tests of thyroid function (TSH, T3, and T4)
- CMV antibody (if negative at baseline)
- Pregnancy test for women of childbearing potential (serum)
- Performance status: ECOG for subjects > 16 years of age or Lansky score for subjects 12 to 16 years of age
- **CCI** [REDACTED]
[REDACTED]
- **CCI** [REDACTED]
- **Only if within 30 days from the last dose of tablecleucel:** **CCI** [REDACTED]
[REDACTED]
[REDACTED]

- Radiographic assessments (including CT with contrast or MRI) as described in Section 7.1

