Treatment and consolidation cycles (21-day): Day 1, Day 8 (± 2), Day 15 (± 2) and response assessment at the observation visit within 7 days after Day 15, except no response assessment after Treatment Cycle 1 Day 15

Observation: between Days 16 to 21 of each treatment/consolidation cycle

Maintenance cycles (84-day): Day 1, Day 21 (± 2), Day 42 (± 2), Day 63 (± 2), and Day 77 (± 2) until a total of 35 pembrolizumab infusions (including for treatment, consolidation, and maintenance) have been given

End-of-Treatment Visit: 30 \pm 5 days after last dose (tabelecleucel and/or pembrolizumab) and for subjects who discontinue early

Quarterly Follow-up: every 90 \pm 14 days after last dose (tabelecleucel and/or pembrolizumab) for 12 months or until disease progression. The last quarterly follow-up visit will be considered the end-of-study for the subject.

- b) High resolution HLA typing includes HLA markers A, B, C, DRB1, and DQB1.
- c) CMV antibody should be assessed at the end-of-treatment visit only if the subject was negative at baseline.
- d) Pregnancy test within 72 hours prior to beginning Cycle 1 Day 1 and at EOT for women of childbearing potential only. Additional pregnancy testing may be conducted as per local regulations, where applicable.
- e) Measure weight and height at screening only; for all other visits, measure weight only.
- f) Vital signs include body temperature, BP, HR, and respiratory rate.
- g) When 2 investigational products are administered on the same day, measure vital signs immediately before and within 10 minutes after the first (pembrolizumab) infusion, and immediately before, within 10 minutes, and at 1 hour (\pm 10 minutes) after the second (tabelecleucel) infusion. The second infusion (tabelecleucel) will only be administered if no infusion reactions related to pembrolizumab are observed/reported or in the case of such a reaction,

Evaluation	Inventory Check ^a	Screening ^a	Treatment/Consolidation Cycles with Observation (21-day) ^a				Maintenance Cycles with Observation (84-day) ^a			EOT Visit ^a	Quarterly Follow-up ^a
			Day 1	Day 8	Day 15	Day 21	Day 1	Days 21, 42, 63	Day 77		
the subject has recovered. For Cycle 1 Day 1 (the initial investigational product exposures), also measure vital signs 2 hours (\pm 10 minutes) after initiation of the second (tabelecleucel) infusion. If the subject experiences symptoms/signs of an infusion reaction, follow-up may be longer, as clinically indicated.											

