### **11.2.2 Treatment-Emergent Laboratory Abnormalities**

Treatment-emergent laboratory abnormalities are defined as values that increase by at least 1 toxicity grade from baseline at any postbaseline time point, up to and including the date of last dose of study treatment plus 30 days. If the relevant baseline laboratory value is missing, any abnormality of at least grade 1 observed within the time frame specified above will be considered treatment-emergent.

Treatment-emergent laboratory abnormalities will be summarized for the selected laboratory parameters.

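### The laboratory cut-off at last dose plus 30 days excludes End-of-Treatment samples that the protocol allows up to Day 35

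*SAP*

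**What the plan says.** SAP section 11.2.1 restricts the descriptive laboratory summaries by collection date: they "will include only data collected up to the last dose of study treatment plus 30 days". The same section undertakes that actual values and changes from baseline "will be presented for each scheduled assessment time point". It adds minimum and maximum post-baseline values, and it states that "grade shifts from baseline to the worst on-treatment value will be summarized for selected lab parameters". Section 11.2.2 defines a treatment-emergent laboratory abnormality as a rise of at least one grade at any post-baseline time point, "up to and including the date of last dose of study treatment plus 30 days".

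Protocol section 6.5 states: "An End-of-Treatment visit will be performed 30 ± 5 days after the last dose of investigational product". Hematology and full chemistry are required at that visit. The procedural notes to the schedule in section 15.1 repeat the window: 30 ± 5 "days after last dose (tabelecleucel and/or pembrolizumab) and for subjects who discontinue early".

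Both rules run from the same date. SAP section 6.1 defines study treatment as tabelecleucel and/or pembrolizumab, the products that anchor the End-of-Treatment visit. The visit-window text in the SAP (6.4) assigns data to nominal visits only where nothing else is specified, and it makes no exception for the End-of-Treatment panel.

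**The concern.** The target day of the visit is the last day the SAP will accept. A subject seen one day after target is within the protocol but outside the analysis.

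The visit matters because it is the only scheduled routine safety laboratory check after treatment ends; Protocol section 6.6 lists no laboratory panel during quarterly follow-up. Protocol section 5.2.5.1 warns that immune-related events can appear months after the last pembrolizumab dose. The SAP also treats one visit in two ways. Section 11.4 summarizes vital signs and worst post-baseline ECOG with no stated 30-day limit, so a Day 33 visit would supply those tables but not the laboratory tables.

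The exposure is greatest for subjects who stop early. Protocol section 5.2.3 withdraws any subject with a DLT from both products. If that happens before Cycle 1 Day 15, the End-of-Treatment panel is the only scheduled post-baseline chemistry.

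**Working it through.** **1. Days lost.** The permitted days run from 30 − 5 = 25 to 30 + 5 = 35, which is 11 days. The SAP keeps days up to 30. Days 31, 32, 33, 34 and 35 are excluded: 5 of 11. This is a share of permitted days, not of visits, because the documents give no visit dates.

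**2. Tests lost per affected subject.** The SAP appendix lists 14 tests for by-visit summary. The End-of-Treatment panel (Protocol 6.5 and 7.2.1) covers 8 in hematology (leukocytes, platelets, neutrophils, lymphocytes, hemoglobin, monocytes, eosinophils, basophils) and 5 in chemistry (creatinine, total bilirubin, AST, ALT, alkaline phosphatase). 8 + 5 = 13, all except LDH. Footnote m in Protocol 15.1 gives a shorter full panel without the four liver tests. On that reading the count would be 13 − 4 = 9, but it conflicts with 6.5 and 7.2.1.

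**3. What changes in which table.** Four constructed subjects, each with baseline grade 0. The worst-grade comparison assumes that the sample would count as *on-treatment*.

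| Earlier worst grade | End-of-Treatment sample | End-of-Treatment row | Worst grade, cut at +30 vs +35 | Treatment-emergent, cut at +30 vs +35 |
|---|---|---|---|---|
| 1 | Day 33, grade 0 | lost | 1 vs 1 | yes vs yes |
| 2 | Day 33, grade 2 | lost | 2 vs 2 | yes vs yes |
| 0 | Day 33, grade 2 | lost | 0 vs 2 | no vs yes |
| 0 | Day 29, grade 2 | kept | 2 vs 2 | yes vs yes |

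The loss from the row follows for every Day 31–35 sample. The other tables move only in the third case, where the excluded value would be decisive.

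**4. How often the value could be decisive.** This depends on *k*, the number of scheduled post-baseline panels before End-of-Treatment. Protocol 6.3.1 schedules panels on Day 1 of each 21-day cycle. Section 6.3.2 adds "Cohort 1, Day 15 only" panels. Section 6.4 gives one panel per maintenance pembrolizumab infusion. Cycle 1 Day 1 is baseline (SAP 6.1).

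- After *c* full cycles, *k* = 2*c* − 1.
- After the full course, *k* = 7 + (35 − 4) = 38.

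Assume, for illustration, no trend over time and no ties. The chance that the End-of-Treatment value is a new maximum for a given test is then 1/(*k* + 1), and the same holds separately for a new minimum.

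| Treatment received | *k* | Chance of a new maximum |
|---|---|---|
| Stops before Cycle 1 Day 15 | 0 | no other scheduled post-baseline chemistry value |
| 1 full cycle | 1 | 1/2 = 50% |
| 2 full cycles | 3 | 1/4 = 25% |
| 4 full cycles | 7 | 1/8 = 12.5% |
| Full 35-infusion course | 38 | 1/39 = 2.6% |

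Under the same assumption, a new worst grade or a first grade increase is no more likely than this, since it must also cross a grade limit. Unscheduled draws and the pre-biopsy hematology panel in PD-1/PD-L1 failures are not counted; they would lower the chances.

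**5. Number of subjects.** The SAP introduction gives 12 enrolled, so the range is 0 to 12. If each End-of-Treatment visit independently had probability *p* of falling on Days 31–35, the expected number is 12*p* and the chance of at least one is 1 − (1 − *p*)^12. These values of *p* are assumptions:

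- *p* = 0.10: 1.2 subjects, 72%
- *p* = 0.25: 3.0 subjects, 97%
- *p* = 0.50: 6.0 subjects, above 99.9%

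Each lost subject is up to 1/12 = 8.3% of the End-of-Treatment row.

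**The case against.** **The SAP describes this visit as falling 30 days after the last dose (section 2.3) and uses nominal visits, so the limit may have been meant to admit it.** That may have been the intention. But the limit in 11.2.1 is worded on the date of collection, and the nominal-visit rule gives way where something else is specified. As written, a Day 33 sample is out.

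**The 30-day limit is a coherent convention.** It matches the exposure period (SAP 6.1), the general TEAE window (SAP 11.1) and the collection of AEs regardless of relatedness (Protocol 8.5). This stands as a reason to keep 30 days as the default. It does not settle the matter, because the TEAE definition already goes past Day 30 for related events. A related Day 33 ALT rise could be a TEAE and yet be missing from the laboratory abnormality table.

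**AE reporting catches what matters.** This is largely right. Clinically meaningful values must be reported as AEs (Protocol 8). After Day 30, events at least possibly related are still collected. SAEs and AEs of special interest, including the hepatic criterion, are reportable to Day 90, or to 30 days after cessation if new therapy starts and that is shorter. What remains is a non-serious abnormality not judged possibly related. SAP 11.2 names no laboratory listing for it, whereas 11.4 names one for vital signs. A listing may exist in table shells that are not in the documents.

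**A subject with an early DLT will probably have unscheduled draws.** This is also fair. SAP 11.2.1 admits those to the minimum/maximum and worst-grade summaries, so zero scheduled panels need not mean zero values. They do not enter the by-visit summary. The SAP's wording also suggests that no de-escalation took place, which under Protocol 3.5 would mean at most 3 DLTs among the 12 subjects.

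**The probabilities rest on an assumption that is doubtful after stopping for toxicity or progression.** Agreed. They show only how the conditional effect shrinks with longer treatment.

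**Conclusion.** The concern holds. As written, the SAP discards End-of-Treatment laboratory samples that comply with the protocol if they are drawn on Days 31 to 35. Each affected subject is missing from the End-of-Treatment row for 13 of 14 tests, taking the panel from Protocol 6.5 and 7.2.1. Effects on the other laboratory tables are conditional, and they are most likely in subjects with few earlier panels.

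The shift table carries a further uncertainty. The SAP does not define *on-treatment*, and 11.2.1 refers both to the worst on-treatment value and to the worst post-baseline grade.

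The consequence is limited to descriptive laboratory tables in a terminated study of 12 subjects. DLT and ORR analyses and the reporting of related AEs, SAEs and AEs of special interest are unaffected. The number of subjects involved cannot be derived from the documents and may be zero; nor do they say whether anyone stopped before Cycle 1 Day 15. The point is worth correcting because correction is cheap, not because the main results are at risk.

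**What to change.** In SAP 11.2.1 and 11.2.2, keep last dose plus 30 days as the default and add a clause such as: *plus the nominal End-of-Treatment sample, if drawn within its protocol window (up to last dose plus 35 days) and before any new anti-NPC therapy starts.* In 11.2.1, state whether this sample counts toward the worst on-treatment value. List every laboratory result excluded by the date rule or the new-therapy rule. With this clause, none of the 11 permitted days is excluded by the date rule alone.

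The cost is one clause in each of two sections, one clarifying sentence and one listing, with no new data. SAP section 8 already uses the start date of new anti-NPC therapy for disease assessments, although 11.3 makes the summary of such therapy conditional on data being available. If that start date is missing, a Day 31–35 sample could be included wrongly.

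The other drawback is that the laboratory window may run up to 5 days past the exposure and general TEAE windows. An unrelated late abnormality could then be treatment-emergent in the laboratory table but not in the AE table, and abnormality counts may rise slightly. A table footnote can explain this.
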